9.1 Informed Consent

Before performing any study-related procedures, the Investigator (or designee) will obtain written informed consent from the patient.

9.2 Study Procedures

Assessments and their timing are to be performed as outlined in the Schedule of Assessments (Table 4). Section 11.5 specifies laboratory assessment samples to be obtained.

Assessments and procedures scheduled at the visit where study drug is administered should be performed before administration of treatment unless otherwise indicated in the Schedule of Assessments (Table 4).

Efficacy/pharmacodynamic assessments are described in Section 100 and include evaluation of anti-coagulation effect via assessment of ACT and aPTT; and anti-platelet effect via assessment of PA.

Safety assessments are described in Section 111 and include vital signs, physical examinations, ECGs, laboratory assessments, AEs, MACE, and major bleeding events.

The Investigator may, at his/her discretion, arrange for a patient to have an unscheduled assessment, especially in the case of AEs that require follow-up or are considered by the Investigator to be possibly related to the use of study drug. The unscheduled visit page in the eCRF must be completed.

Study discontinuation procedures are described in Section 7.3.

9.2.1 Screening on Admission

Screening procedures will follow the normal pre-PCI evaluation per local standard of care, providing that all protocol-specific testing and procedures are completed before the administration of MT1002. All standard of care laboratory assessments and ECGs will be performed at the study site.

Unless specifically noted otherwise (or required by regulation), all study assessment time points are relative to initial intravenous injection of MT1002.

- Obtain informed consent before any protocol-specific procedures.
- Record demographic data, such as date of birth or age (according to applicable regulations), ethnic origin, and sex.
- Collect relevant medical and surgical history, including a detailed allergy history, concomitant illnesses/diseases, and concomitant medications (including cardiac and noncardiac medications) at the time of admission.
- Perform a full physical examination; record body weight and height, and body mass index (BMI).
- Record vital signs (body temperature, respiration rate, heart rate, and systolic and diastolic blood pressure).
- Perform a 12-lead ECG.
- Collect blood samples for hematology, coagulation, and clinical chemistry (refer to the Schedule of Assessments [Table 4] and Section 11.5 for parameters included)
 - CK-MB, cardiac troponin I (troponin T can be measured if the local site does not have the troponin I test)
 - ACT, aPTT, PT, TT, FIB, INR
 - Hematocrit, hemoglobin, platelet count, red blood cell (RBC) and white blood cell (WBC) counts
 - Serum chemistry including lipid panel and glycosylated hemoglobin (HbA1c)
- Perform a PA (by PFA100 or PFA200)

- Locally perform serum or urine pregnancy test on all WOCPB who have not been postmenopausal for at least 1 year or sterilized.
- Assign or confirm, if already assigned, dual antiplatelet therapy. If not already given, administer a loading dose of the dual antiplatelet therapy of aspirin and clopidogrel (or Ticagrelor or Prasugrel) as indicated in the Schedule of Assessments (Table 4).
- Record any AEs that have occurred and any changes in concomitant medication since signing of the informed consent.
- Obtain CRUSADE bleeding risk score.
- Assess for eligibility (against the inclusion and exclusion criteria). Indication for early PCI should be confirmed in accordance with latest international or local guidelines^{3,4}
 - Established diagnosis of NSTEMI based on elevated cardiac biomarkers
 - Dynamic ST/T-changes (symptomatic or silent)
 - Global Registry of Acute Coronary Events (GRACE) score >140

9.2.2 Pre-percutaneous Coronary Intervention Day 1 (Baseline)

Enrollment should occur as close to the planned start of PCI as possible, and MT1002 dosing should be started as close to the actual start of PCI as possible. MT1002 should be initiated during diagnostics angiography when indication for PCI is confirmed, provided the early PCI is indicated right after the coronary angiography. Study drug should be administered in the catheterization lab.

Either radial access/distal radial access PCI or femoral access PCI will be used in this study. It is up to the discretion of the Principal Investigator what type of stent(s) will be used.

- Confirm that diagnostic catheterization indicates the need for PCI. The Investigator's interpretation of the diagnostic angiogram, TIMI flow grade, the treatment plan, and if the patient remains eligible to continue the study should be recorded.
- Record vital signs (body temperature, respiration rate, heart rate, and systolic and diastolic blood pressure).
- Perform a 12-lead ECG.
- Confirm all screening procedures have been completed and that the patient meets all other eligibility requirements and record patient enrollment with identification of allocated study drug vial.
- Record all changes in concomitant medications including cardiovascular, antiplatelet, anticoagulant and diabetic medications administered since screening.
- Obtain pre-dose baseline central cardiac biomarkers (troponin I [troponin T can be measured if the local site does not have the troponin I test], and CK-MB) immediately before PCI; and hemoglobin, hematocrit, platelet count, and RBC and WBC counts; coagulogram (ACT, aPTT, PT, TT, FIB, INR according to the time points in the Schedule of Assessments [Table 4] and Table 5), Pharmacokinetic blood sampling (according to the time points in the Schedule of Assessments [Table 4] and Table 5).

Additional ACT test can be performed if MT 1002 dose is adjusted. The ACT test value and time of test will be recorded in eCRF. These blood samples may be obtained either peripherally or through the arterial sheath.

- Collect PK plasma samples according to the time points in the Schedule of Assessments (Table 4) and Table 5.
- Perform a PA (by PFA100 or PFA200) according to the time points in the Schedule of Assessments (Table 4) and Table 5.
- Administer study drug via IV access before the PCI and record time of dosing in the eCRF. Study drug should be administered in catheterization lab as close to randomization and the start of the PCI procedure as possible.
- Conduct a visual bleeding inspection and assess bleeding AEs according to the BARC criteria; record any patient-reported bleeding.
- Record any other AEs that have occurred.

9.2.3 During Percutaneous Coronary Intervention, Day 1

Either radial access/distal radial access PCI or femoral access PCI will be used in this study. It is up to the discretion of the Principal Investigator what type of stent(s) will be used.

- Conduct the PCI procedure per local standard of care.
- Record TIMI flow grade post PCI.
- Patients who fail to achieve ACT target of 200 to 300 sec with MT1002 (within 30 minutes after MT1002 infusion initiation) before PCI will be switched to standard of care (UFH or bivalirudin, see Section 8.5.1).
- Patients who achieve ACT target of 200 to 300 sec with MT1002 (within 30 minutes after MT1002 infusion initiation) before PCI should continue the study drug infusion for 4 ± 0.5 hours after infusion start.
- Monitor patients for potential AEs, including allergic reactions during the MT1002 administration.
- Record vital signs (body temperature, respiration rate, heart rate, and systolic and diastolic blood pressure).
- Record any procedural complications, as well as any other AEs
 - Glycoprotein IIb/IIIa inhibitors may be used for procedural or angiographic complications only (dosing per local standard of care, see Section 8.5.1)
 - In those patients who experience significant intracoronary thrombosis during the procedure, or experience acute thrombosis after the procedure, heparin bail out may be administered (see Section 8.5.1).
- Perform a PA (by PFA100 or PFA200) according to the time points in the Schedule of Assessments (Table 4) and Table 5.

- Obtain central cardiac biomarkers (troponin I [troponin T can be measured if the local site does not have the troponin I test], and CK-MB) according to the time points in the Schedule of Assessments (Table 4) and Table 5.
- Obtain coagulogram (ACT, aPTT, PT, TT, FIB, INR according to the time points in the Schedule of Assessments [Table 4] and Table 5), hemoglobin, hematocrit, platelet count, RBC, and WBC counts.
- Obtain PK samples according to the time points in the Schedule of Assessments (Table 4) and Table 5.
- Conduct a visual bleeding inspection and assess bleeding AEs according to the BARC criteria; record any patient-reported bleeding.
- Record all changes in concomitant medications.
- Obtain a copy of the PCI procedure report and record information about index-procedure (e.g., but not limited to vascular access, lesions treated, stents used, procedure result). Successful treatment with PCI is defined as achievement of < 30% residual diameter stenosis of all treated lesions assessed by visual inspection or quantitative coronary angiography, without an in-hospital major adverse cardiac event (death, MI or repeat coronary revascularization of the target lesion).

9.2.4 Post Percutaneous Coronary Intervention, Day 1

- Record end of PCI time in the eCRF. End of procedure is defined as the date/time when the last coronary catheter (all catheters other than arterial sheath or intra-aortic balloon positioning) is removed from the body.
- Continue MT1002 infusion for 4 hours after infusion start (including post-PCI).
- Remove the sheath approximately 3 hours after MT1002 infusion is complete. Record sheath removal time in the eCRF.
- Perform a brief physical examination.
- Record vital signs (body temperature, respiration rate, heart rate, and systolic and diastolic blood pressure).
- Perform a 12-lead ECG.
- Perform a PA (by PFA100 or PFA200) according to the time points in the Schedule of Assessments (Table 4) and Table 5.
- Collect blood samples for hematology, coagulogram, and cardiac biomarkers (refer to Section 11.5 for parameters included)
 - CK-MB, cardiac troponin I (troponin T can be measured if the local site does not have the troponin I test) according to the time points in the Schedule of Assessments (Table 4) and Table 5
 - ACT, aPTT, PT, TT, FIB, INR as per time points in the Schedule of Assessments (Table 4) and Table 5
 - Hematocrit, hemoglobin, platelet count, RBC and WBC counts according to the time points in the Schedule of Assessments (Table 4)

This document is confidential.

- Obtain PK samples according to the time points in the Schedule of Assessments (Table 4) and Table 5.
- Record all changes in concomitant medications.
- Conduct a visual bleeding inspection and assess bleeding AEs according to the BARC criteria; record any patient-reported bleeding
 - Immediately upon achievement of hemostasis, with time of complete hemostasis recorded on the eCRF;
 - Thereafter, per local standard of care
- Record any other AEs that have occurred.

9.2.5 Day 2

- Perform a brief physical examination.
- Record vital signs (body temperature, respiration rate, heart rate, and systolic and diastolic blood pressure).
- Perform a 12-lead ECG.
- Collect blood samples for hematology, serum chemistry, coagulogram, and cardiac biomarkers (refer to the Schedule of Assessments [Table 4] and Table 5; and Section 11.5 for parameters included)
 - CK-MB, cardiac troponin I (troponin T can be measured if the local site does not have the troponin I test)
 - ACT, aPTT, PT, TT, FIB, INR
 - Hematocrit, hemoglobin, platelet count, RBC and WBC counts
 - Serum chemistry
- Perform a PA (by PFA100 or PFA200) according to the time points in the Schedule of Assessments (Table 4) and Table 5.
- Obtain PK samples according to the time points in the Schedule of Assessments (Table 4) and Table 5.
- Record all changes in concomitant medications.
- Continue dual antiplatelet therapy with aspirin and clopidogrel (or Ticagrelor or Prasugrel).
- Conduct a visual bleeding inspection and assess bleeding AEs according to the BARC criteria; record any patient-reported bleeding.
- Record any other AEs that have occurred.

Patients will be discharged from the hospital when they are stable according to local standard of care.

9.2.6 Day 14±1, Day 30±2 (End of Study)

- Perform a brief physical examination.

- Record vital signs (body temperature, respiration rate, heart rate, and systolic and diastolic blood pressure).
- Perform a 12-lead ECG.
- Collect blood samples for hematology, serum chemistry, coagulogram, and cardiac biomarkers (refer to the Schedule of Assessments [Table 4] and Table 5; and Section 11.5 for parameters included)
 - CK-MB, cardiac troponin I (troponin T can be measured if the local site does not have the troponin I test)
 - ACT, aPTT, PT, FIB, TT, INR
 - Hematocrit, hemoglobin, platelet count, RBC and WBC counts
 - Serum chemistry including lipid panel (lipid panel on Day 30 only)
- Perform a PA (by PFA100 or PFA200).
- Locally perform serum or urine pregnancy test (only Day 30) on all WOCPB who have not been postmenopausal for at least 1 year or sterilized.
- Record all changes in concomitant medications.
- Continue dual antiplatelet therapy with aspirin and clopidogrel (or Ticagrelor or Prasugrel) (Day 30: confirm continuation of dual antiplatelet therapy with aspirin and clopidogrel (or Ticagrelor or Prasugrel)).
- Conduct a visual bleeding inspection and assess bleeding AEs according to the BARC criteria; record any patient-reported bleeding.
- Record any other AEs that have occurred.

10 EFFICACY/PHARMACODYNAMIC ASSESSMENTS

The Schedule of Assessments (Table 4) outlines the efficacy assessments to be performed throughout the study and their timing.

10.1 Anti-coagulation effect and anti-platelet effect

Anti-coagulation effect and anti-platelet effect will be evaluated using standard local lab equipment and PFA100 or PFA200 (PA).

11 SAFETY ASSESSMENTS

Safety assessments (vital signs, physical examinations, ECG recording, AEs, MACE, major bleeding events, clinical laboratory results [serum chemistry; hematocrit, hemoglobin, platelet count, RBC and WBC counts]) are to be performed at protocol-specified visits, as noted in the Schedule of Assessments (Table 4).

11.1 Medical History

Significant medical history will be recorded at Screening (upon admission on Day 1). Investigators should document the occurrence, signs, and symptoms of the patient's relevant preexisting conditions, including all relevant prior significant illnesses and surgery; the focus should be on coronary artery disease. Additional preexisting conditions present at the time when informed consent is given and up to the time of dosing are to be regarded as concomitant. Medical history will include alcohol consumption and smoking history, if applicable.

Illnesses first occurring or detected during the study and/or worsening of a concomitant illness during the study are to be documented as AEs on the eCRF in accordance with Section 11.6. All changes not present at Screening/Baseline or described in the past medical history and identified as clinically noteworthy must be recorded as AEs.

Additionally, demographic data will be collected for all patients and include date of birth or age according to applicable regulations, sex, race, and ethnicity.

11.2 Vital Signs

Vital signs (body temperature, respiration rate, heart rate, and systolic and diastolic blood pressure measurements) will be evaluated at the visits indicated in the Schedule of Assessments (Table 4). All vital signs will be measured after the patient has been resting in a semi-supine position for at least 5 minutes. Blood pressure measurements are to be taken in the same arm for the duration of the study. Body weight and height (without shoes) and body mass index will be recorded at Screening only.

Vital sign measurements will be repeated if clinically significant or machine/equipment errors occur. Out-of-range blood pressure, respiratory rate, or heart rate measurements will be repeated at the Investigator's discretion. Any confirmed clinically significant vital sign measurements must be recorded as AEs.

11.3 Physical Examination

A complete physical examination (general appearance, head, eyes, ears, nose and throat; and cardiovascular, respiratory, gastrointestinal, dermatological, neurological, musculoskeletal, lymphatic, and other systems at the discretion of the Investigator) will be performed by a physician on Admission Day 1. Brief physical examination should be performed on all other visits from Post-PCI Day 1 onwards and includes general appearance, as well as cardiovascular, respiratory, gastrointestinal, and other systems at the discretion of the Investigator.

11.4 Electrocardiograms

A 12-lead, resting ECG will be obtained at the visits indicated in the Schedule of Assessments (Table 4).

At Screening, the Investigator will examine the ECG traces for signs of cardiac disease that could exclude the patient from the study. An assessment of normal or abnormal will be recorded; if the ECG is considered abnormal, the abnormality will be documented on the eCRF. ECGs will be repeated if clinically significant abnormalities are observed or artifacts are present. All ECGs will be read locally.

11.5 Laboratory Assessments

The hematology and clinical chemistry laboratory analyses will be performed at local laboratories. Reference ranges will be supplied by local laboratories and used by the Investigator to assess the laboratory data for clinical significance and pathological changes.

Laboratory assessment samples (Table 6) are to be obtained at designated visits as detailed in the Schedule of Assessments (Table 4).

Table 6 Laboratory Assessments

Hematology	Serum Chemistry
Hct Hb Platelet count RBC count WBC count with differential	ALT AST BUN or urea Creatinine Creatine kinase and subtypes Electrolytes (sodium, potassium) Glucose LDH Total bilirubin Direct bilirubin Total protein Lipid panel eGFR HbA1c
Coagulation	Others
PT Activated PTT ACT TT FIB INR PA (by PFA100 or PFA200)	CK-MB Cardiac troponin I or troponin T (troponin T can be measured if the local site does not have the troponin I test)
Pregnancy test: A pregnancy test (serum or urine) will be performed on all women of childbearing potential at Screening and at End of Study (Day 30±2).	

Abbreviations: ACT, activated clotting time; ALT, alanine aminotransferase; AST, aspartate aminotransferase; BUN, blood urea nitrogen; CK, creatine kinase; eGFR, estimated glomerular filtration rate; Hb, hemoglobin; HbA1c, glycosylated hemoglobin; Hct, hematocrit; LDH, lactate dehydrogenase; PT, prothrombin time; PTT, partial thromboplastin time; RBC, red blood cell; WBC, white blood cell.

Blood samples will be analyzed at a local laboratory facility. All laboratory reports must be reviewed, signed, and dated by the Investigator. A legible copy of all reports must be filed with both the patient's eCRF and medical record (source document) for that visit. Any laboratory test result considered by the Investigator to be clinically significant should be considered an AE (clinically significant AEs include those that require an intervention). Clinically significant abnormal values occurring during the study will be followed up until repeat test results return to normal, stabilize, or are no longer clinically significant.

11.6 Adverse Events

11.6.1 Adverse Events

An AE is any symptom, physical sign, syndrome, or disease that either emerges during the study or, if present at Screening, worsens during the study, regardless of the suspected cause of the event. All medical and psychiatric conditions (except those related to the indication under study)

present at Screening will be documented in the medical history eCRF. Changes in these conditions and new symptoms, physical signs, syndromes, or diseases should be noted on the AE eCRF during the rest of the study. Clinically significant laboratory abnormalities should also be recorded as AEs.

Anticipated AEs

Anticipated AEs for this study population based on the results from the completed Phase 1 healthy volunteer study include bleeding (see also Section 11.6.3), allergic reactions, and headache.

Drug-related AEs which occurred in the completed Phase 1 study included headache, dizziness, discolored feces, mouth hemorrhage, injection site bruising and injection site nodule, and injection site hemorrhage.

Reporting of AEs

Patients will be instructed to report AEs at each study visit. All AEs are to be followed up until resolution or a stable clinical endpoint is reached.

Each AE is to be documented on the eCRF with reference to date of onset, duration, frequency, severity, relationship to study drug, action taken with study drug, treatment of event, and outcome. Furthermore, each AE is to be classified as being serious or nonserious. Changes in AEs and resolution dates are to be documented on the eCRF.

For the purposes of this study, the period of observation for collection of AEs extends from the time the patient gives informed consent until the end of study visit. Follow-up of the AE, even after the date of study drug completion, is required if the AE persists until the event resolves or stabilizes at a level acceptable to the Investigator.

When changes in the intensity of an AE occur more frequently than once a day, the maximum intensity for the event should be noted. If the intensity category changes over a number of days, then those changes should be recorded separately (with distinct onset dates).

Specific guidelines for classifying AEs by intensity and relationship to study drug are given in Table 7 and Table 8.

Table 7 Classification of Adverse Events by Intensity

Severity	Description
Mild	Awareness of signs and symptoms, but are easily tolerated; are of minor irritant type; causing no limitations of usual activities. Signs or symptoms may require minor action.
Moderate	Discomfort severe enough to cause some limitations of usual activities and may require action.

Severity	Description
Severe	Incapacitating with inability to carry out usual activities or significantly affects clinical status, and requires specific action and/or medical attention.

Table 8 Classification of Adverse Events by Relationship to Study Drug


UNRELATED: This category applies to those AEs that are clearly and incontrovertibly due to extraneous causes (disease, environment, etc).
 
UNLIKELY: This category applies to those AEs that are judged to be unrelated to the study drug/procedure but for which no extraneous cause may be found. An AE may be considered unlikely to be related to study drug/procedure if or when it meets 2 of the following criteria: (1) it does not follow a reasonable temporal sequence from administration of the test drug/study procedure; (2) it could readily have been produced by the patient's clinical state, environmental or toxic factors, or other modes of therapy administered to the patient; (3) it does not follow a known pattern of response to the test drug/study procedure; or (4) it does not reappear or worsen when the study drug/procedure is readministered.
 
POSSIBLY: This category applies to those AEs for which a connection with the test drug/study procedure administration appears unlikely but cannot be ruled out with certainty. An AE may be considered possibly related if or when it meets 2 of the following criteria: (1) it follows a reasonable temporal sequence from administration of the test drug/study procedure; (2) it could not readily have been produced by the patient's clinical state, environmental or toxic factors, or other modes of therapy administered to the patient; or (3) it follows a known pattern of response to the test drug/study procedure.
 
PROBABLY: This category applies to those AEs that the Investigator feels with a high degree of certainty are related to the test drug/study procedure. An AE may be considered probably related if or when it meets 3 of the following criteria: (1) it follows a reasonable temporal sequence from administration of the study drug/procedure; (2) it could not be reasonably explained by the known characteristics of the patient's clinical state, environmental or toxic factors, or other modes of therapy administered to the patient; (3) it disappears or decreases on cessation or reduction in dose (note that there are exceptions when an AE does not disappear upon discontinuation of the study drug, yet drug-relatedness clearly exists; for example, as in bone marrow depression, fixed drug eruptions, or tardive dyskinesia); or (4) it follows a known pattern of response to the test drug/study procedure.
 
DEFINITELY: This category applies to those AEs that the Investigator feels are incontrovertibly related to test drug/study procedure. An AE may be assigned an attribution of definitely related if or when it meets all of the following criteria: (1) it follows a reasonable temporal sequence from administration of the study drug/procedure; (2) it could not be reasonably explained by the known characteristics of the patient's clinical state, environmental or toxic factors, or other modes of therapy administered to the patient; (3) it disappears or decreases on cessation or reduction in dose and recurs with re-exposure to drug (if rechallenge occurs); and (4) it follows a known pattern of response to the test drug/study procedure.

--

Abbreviation: AE, adverse event.

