6 INVESTIGATIONAL PLAN

6.1 Description of Overall Study Design and Plan

This is an open-label, sequential-dose escalation/de-escalation trial testing 3 dose levels of MT1002 in patients undergoing PCI due to ACS with NSTEMI. Three doses of MT1002 will be sequentially tested in cohorts of 6 patients each to achieve target ACT.

Pre-specified dose escalation/de-escalation/stopping/continuation rules for the patient cohorts are shown in Table 1 below.

Table 1 Rules for Dose Escalation/De-Escalation/Stopping/Continuation

Continue to next higher dose group if:	Stop study drug infusion temporarily in an individual patient if:	Stop dose group and de-escalate according to protocol if:	Continue the same dose in the next patient cohort (to get more data for initial dose) if:	Stop the study if:
$\leq 2/6$ pat peak ACT > 300	Any ACT > 350 or < 180	$\geq 3/6$ pat peak ACT > 300	$\leq 3/6$ pat peak ACT > 300	> 3/6 pat peak ACT > 350
≥ 3 pts. peak ACT < 200 (Cohort 2)				AND
$\leq 1/6$ pat with BARC 3 to 5	BARC 3 to 5	$\geq 2/6$ pat with BARC 3 to 5	$\leq 1/6$ pat with BARC 3 to 5	> 2/6 pat with BARC 3 to 5
				OR
No SAE due to study drug	Any AE/SAE due to study drug that requires switching patient to standard of care	$\geq 2/6$ SAEs due to study drug	No SAE due to study drug	$\geq 2/6$ SAEs due to study drug

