14.4 Safety Analysis

All reported AEs will be coded using the Medical Dictionary for Regulatory Activities (MedDRA), version used will be the current one at the time of analysis. The incidence of TEAEs

This document is confidential.

(events with onset dates on or after the start of the study drug) will be included in incidence summary tables. Events with missing onset dates will be included as treatment-emergent. If a patient experiences more than 1 occurrence of the same AE, the occurrence with the greatest severity and the closest association with the study drug will be used in the summary tables. The major bleeding events, minor bleeding events, MACE within 30 days, and AEs of interest will be summarized by MedDRA system organ class and preferred term, and by cohort and overall; SAEs and AEs causing study discontinuation will also be summarized. All AEs will be listed by patient, along with information regarding onset, duration, relationship and severity to study drug, action taken with study drug, treatment of event, and outcome.

Clinical laboratory data and vital signs will be summarized using descriptive statistics, including mean values and mean change from baseline values, as well as numbers of patients with values outside limits of the normal range at each time point.

12-lead ECGs will be summarized descriptively. The noteworthy QTcF interval (>450 , >480 , >500 msec) and noteworthy change from baseline (>30 and >60 msec) will also be summarized.

Summary tables will be provided for concomitant medications initiated during the study period.

Physical examination results will be listed.

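### The scale for relationship to study drug also rates relationship to the study procedure, so a PCI complication can be recorded as MT1002-related and could count in the dose and stopping rules

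*Combined protocol and SAP*

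**What the plan says.** Section 11.6.1 has each adverse event recorded with "date of onset, duration, frequency, severity, relationship to study drug, action taken with study drug, treatment of event, and outcome". Relationship to study drug is the only causality item in that list, and the section points to Table 8 for rating it. The table's title agrees: "Table 8 Classification of Adverse Events by Relationship to Study Drug".

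The category texts do not. DEFINITELY reads "This category applies to those AEs that the Investigator feels are incontrovertibly related to test drug/study procedure". PROBABLY covers events that "the Investigator feels with a high degree of certainty are related to the test drug/study procedure". POSSIBLY and UNLIKELY have the same double object. Only UNRELATED is free of it; that category points to extraneous causes, with disease and environment as examples. The criterion on typical response is also double: "it follows a known pattern of response to the test drug/study procedure". One criterion works in the other direction: an event that the patient's clinical state could explain, or "environmental or toxic factors, or other modes of therapy administered to the patient", loses support for relatedness.

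Table 1 in Section 6.1 makes "No SAE due to study drug" a condition both for escalating and for repeating a dose. A limit of two or more over six appears in both the de-escalation column and the study-stop column. For repeated events in one patient, Section 14.4 says that "the occurrence with the greatest severity and the closest association with the study drug will be used in the summary tables".

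**The concern.** One rating is asked to answer two questions. In this trial the drug is started just before PCI, so the two candidate causes coincide in time, and several adverse events of interest (abrupt vessel closure, stent thrombosis, emergency CABG) can arise from either. An investigator who applies Table 8 as worded may give a procedural complication a positive rating, and the database will show it as related to MT1002. The reader of the data cannot undo this, because Section 11.6.1 provides no rating for the procedure.

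At stake are the Table 1 criteria on drug-caused SAEs, which are strict in a cohort of six, and the relationship shown in the Section 14.4 summaries and listings. The primary objective is to find a safe and well tolerated dose, so attribution to the drug is central to what the trial reports.

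**Working it through.** **Step 1. Can a purely procedural event reach a positive rating?** Take a guide-wire dissection with no drug contribution, and apply Table 8 under the two readings that the protocol leaves open.

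| Table 8 element | PCI read as the study procedure | PCI read as other therapy |
|---|---|---|
| Reasonable temporal sequence | Met | Met (the drug starts just before PCI) |
| Known pattern of response | Met, through the procedure | Not met |
| Not explained by other therapy | Arguable | Not met |
| POSSIBLY (2 of 3) | Reached on the first two alone | Not reached |
| PROBABLY (3 of 4) | Reached if the third criterion or the cessation criterion is accepted | Not reached |

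Under the first reading, UNLIKELY does not fit, because it requires a judgement that the event is unrelated to drug and procedure. Under the second, UNLIKELY is available. The same event therefore gets different ratings depending on an undefined term.

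**Step 2. Which reading does the protocol favour?** For PCI as study procedure: Section 9 is headed Study Procedures, Table 4 has a PCI row, and Section 9.2.4 uses end of procedure for the end of the PCI. Against: Section 9.2.3 has PCI carried out under local standard of care. The first reading is reasonable but not settled.

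**Step 3. How large could the effect be?** The plan gives no operating characteristics to reproduce. Inputs: cohort size 6 (Section 6.1); procedural SAE rate p per patient, not given in the documents and assumed here. Further assumptions: every procedural SAE is counted as due to drug, the drug causes none, and patients are independent.

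- At least one affected patient: 1 − (1 − p)^6
- At least two: 1 − (1 − p)^6 − 6p(1 − p)^5
- At least two in one or more of three cohorts: 1 − (1 − q)^3, with q the previous line

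| p | At least one of 6 | At least two of 6 | Two or more in any of three cohorts |
|---|---|---|---|
| 1% | 5.9% | 0.1% | 0.4% |
| 5% | 26.5% | 3.3% | 9.5% |
| 10% | 46.9% | 11.4% | 30.5% |

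For p = 5%: 1 − 0.7351 = 0.265, and 1 − 0.7351 − 0.2321 = 0.033.

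With a true drug SAE rate of 2% and a procedural rate of 10%, the combined rate is 1 − 0.98 × 0.90 = 11.8%. The probabilities are then 52.9% (at least one) and 15.1% (at least two), against 11.4% and 0.6% for the drug alone.

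These figures count patients. The Table 1 row is written as SAEs over six, so if events are counted, one patient with two SAEs would reach the limit and the last two columns would be higher.

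**The case against.** A reader might infer that PCI complications necessarily score as drug-related and thereby drive the dose and stopping decisions. The documents do not support that. Study procedure is never defined as PCI. Table 1 neither cites Table 8 nor says which categories amount to an SAE due to study drug. The Study Management Group, which includes the Medical Monitor and an independent cardiologist, decides in conjunction with the criteria, not automatically by them. Table 8 itself says that an event may be considered related, which leaves room for judgement, and its other-therapy criterion can be used to discount PCI. All of this stands, and it limits the point to what can happen.

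Four further limits also stand:

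- PCI is not performed in every enrolled patient. Those without it are replaced but stay in the safety population.
- An access-site haematoma would be a poor example, because bleeding is an anticipated effect of MT1002. BARC 3 to 5 bleeding also has its own Table 1 row, which counts events whatever their cause.
- Section 14.4 names no table of drug-related events, so an overstatement of toxicity there is indirect, through the rule for selecting the occurrence and the listing of relationship.
- The version 6.0 change summary reports no SAEs in the six Cohort 1 patients. This is weak evidence on the rate: at p = 10%, none in six has probability 0.9^6 = 53.1%.

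The objection does not remove the wording conflict. Judgement by the Study Management Group is a safeguard, but Section 11.6.1 gives the group no procedure rating to work from.

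**Conclusion.** The defect is one of wording and data capture: a scale titled and used for relationship to study drug also admits relationship to the procedure, and no other field separates them. A procedural complication can be rated POSSIBLY or higher on timing plus known pattern, and could then count toward the Table 1 criteria on drug-caused SAEs. That last step needs PCI to be read as the study procedure and a positive rating to be taken as due to study drug; neither is stated.

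The tabulated probabilities are upper-end figures for each assumed rate, because they take misattribution to be complete. The effect on the two-of-six limit is negligible at 1% and material at 10%; the effect on the zero-SAE condition is already visible at 1%. The change should be made because it is cheap and removes an ambiguity in a small cohort, whatever the true rate. The BARC 3 to 5 rows are not affected.

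**What to change.** 1. In Table 8, remove the reference to the procedure from every category and criterion, so that the scale rates MT1002 only.
2. Add a separate eCRF rating for relationship to PCI and vascular access, and define that term. Allow both ratings to be positive for one event.
3. State in Section 6.1 which MT1002 categories count as due to study drug in Table 1, and that the procedure rating is not used there. The sponsor has to choose the categories.
4. State in Section 14.4, and in the SAP that is to supersede the protocol where they differ, that the relationship selected and listed is the MT1002 rating.
5. Separately, the SAE limit in Table 1 is expressed as SAEs over six while the other rows count patients. The sponsor must reconcile the counting unit; no unit or limit is proposed here.

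The cost is one eCRF field, a wording change and a second rating of adverse events already recorded in Cohort 1. Section 8.5.1 already asks investigators for a separate causality assessment of SAEs for the background antiplatelet drugs, and Section 11.6.6 already speaks of drug and procedures as distinct causes. The change does not alter how weakly the cessation criterion discriminates when the infusion ends by design at about four hours; that limit remains.
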